4.2 Recruitment, screening and informed consent procedure

The participating study centers screen their electronic patient records in line with the local regulations on data protection for patients fulfilling the eligibility criteria. Also, GP practices and, depending on the recruitment rate, retirement and nursing homes, patient associations (e.g. Pro Senectute, Spitex), and pharmacies, will be contacted and asked to screen and inform their patients about the possibility to participate in the study. In addition, potentially eligible participants from our previous OPERAM study (59) will be contacted and informed about the possibility to participate in the study. Depending on the recruitment rate, also public advertisement, e.g., in local hospitals and GP practices, magazines, newspapers or public transport might be an option. Each patient fulfilling all eligibility criteria is invited to participate. For screened patients who do not consent to participate, age, gender, eligibility criteria assessment and the reason for not consenting is collected systematically in the eCRF, (without any identifying information) to assess the degree of potential selection bias in the study enrollment process.

The screening and baseline visit is performed at a study site. The informed consent procedure is either performed by a study nurse in a hospital (supervised by a medical doctor) or by a GP. The study nurses are supervised locally by study physicians, who are involved in case of questions that require the expertise of a physician. In addition, study nurses have phone access to the study physicians at the main trial site (Bern). The study nurse/GP explains to each potential participant the nature of the study, its purpose, the procedures involved, the expected duration, the potential risks and benefits, and any discomfort it may entail. Each candidate is informed that the participation in the study is voluntary and that he or she may withdraw from the study at any time and that withdrawal of consent will not affect his or her subsequent medical assistance and treatment. Each candidate has the opportunity to ask questions to a medical doctor if the study nurse performs the inclusion procedure.

Study nurses who are responsible for the informed consent procedure must have a GCP certificate and receive tailored training for their study specific tasks. GPs without GCP certification are provided with a tailored GCP training specific for their limited task within the study, which includes training on patient information and consenting, and on adverse event detection, documentation, and reporting. Since GP practices are distributed all over Switzerland, this training will be provided through video and a written transcript of the key points of the video.

The candidate is informed that his or her medical records are examined by authorised individuals other than their treating physician and that their treating physician(s) and/or pharmacist(s) will be informed about the study participation. They are informed that institutions that provided or will provide medical care for the candidate (such as GP practices, pharmacies, hospitals, retirement or nursing homes) can be contacted during the conduct of the study to obtain medical information. They are also informed that the community of residence can be contacted to obtain a death certificate or information on change of residence.

Each candidate is provided with a participant information sheet and a consent form describing the study and providing sufficient information for the candidate to make an informed decision about his or her participation in the study. Since the study inclusion is under no time pressure, the candidates are given as much time as they deem necessary to consider participating in the study. The consent of a participant is obtained before the participant is submitted to any study procedure.

The consent form is signed and dated by the study nurse/GP at the same time as the participant signs. A copy of the participant information sheet and signed informed consent form is given to the study participant. The consent form is retained as part of the study records. The informed consent process is documented in the patient file of the hospital/GP practice.

For the enrolment of mentally impaired participants, we rely on the procedure of the OPERAM study (59), which has proven itself in the clinical practice and has been approved by the Swiss Ethics Committee (EC) (BASEC Nr. 2016-01200): as the enrolment of a patient with mental impairment (dementia, confusion) is usually limited by the physical absence of the legal representative in hospitals, the informed consent can be given orally in the presence of at least one witness. The witness should be formally independent of the study team. The oral consent can be given by the patient, provided that he/she is able to consent orally and to understand the study participation. If the patient is unable to give his or her consent orally, oral consent can also be obtained over the phone from a legal representative. Written consent from the legal representative is obtained as soon as possible thereafter. Also, in this procedure, patients/legal representatives are given adequate time to consider their decision whether or not to accept participation. This procedure is intended to avoid selection bias of this vulnerable group of patients with mental impairment that is often excluded from clinical trials.

4.3 Study procedures

The expected recruitment period is 36 months. Study subjects remain in the study for the entire duration of the intervention period. Minimum intervention period duration is 12 months, maximum intervention period duration is expected to be 48 months. Mean intervention period is expected to be 24 months.

Outcomes are assessed at each study follow-up. Study personnel contacts the subject, and and/or GPs by phone and will review medical records to obtain information from hospitals and GPs about medical events and concomitant treatment during follow-up. If a subject is unavailable and cannot be reached, or if the subject is mentally not capable to perform the phone interview, a family member and/or a friend not living in the same household will be contacted. For subjects who die during the intervention period, the cause of death based on medical reports, death certificates, and autopsy reports (if available) will be recorded.

After the end of the intervention period, the subjects or, if unavailable, GPs, family members/friends are contacted annually by phone for a follow-up visit for a maximum of 10 years from baseline. The follow-ups after the intervention period are optional, depending on the time and financial resources of the study team. Upon inclusion, patients are asked for a separate consent for data collection after the intervention period.

See chapter 3.2 “Schedule of assessments” for a detailed description of the study procedures.

4.4 Withdrawal and discontinuation

Withdrawal from intervention

For the intervention group (statin discontinuation): If a participant suffers a CV event during the intervention period, restarting a statin is up to the discretion of the treating physician. If a subject would like to restart their statin without CV event (e.g., because of an external lipid measurement), we advise GPs not to restart a statin or other lipid lowering medication, since the evidence for a statin therapy in primary prevention in elderly patients is unclear and currently no clearly defined LDL target for this patient group exist based on trial data. However, the final decision is up to the discretion of the treating physician.

For the control group (statin continuation): If a subject would like to stop their statin (e.g., because of side effects), stopping a statin is up to the discretion of the treating physician and of the patient. Since the currently limited evidence does not show very clear difference in muscle symptom scores between statin and placebo (60), we advise GPs not to prompt statin discontinuation in subjects with muscle symptoms without criteria for myositis (CK > 10 ULN).

The treating physician and the participant are asked to inform the study team about any change regarding lipid lowering medication.

If a subject withdraws from the assigned intervention, follow-up will continue until the end of the trial.

Change in drug dose

Statin doses are monitored during the study. Change in drug dose is at the discretion of the treating physician.

Discontinuation of study

A study participant must be withdrawn from the study if he or she withdraws consent for further study participation. A study participant who discontinues study participation prematurely is defined as dropout if the participant has already been randomized.

No replacement of participants discontinuing study intervention or study participation is foreseen. Any samples and data collected until study withdrawal will remain coded for the analysis. It is not possible to anonymize the collected study data upon withdrawal.

4.5 Concomitant care

There are no restrictions on concomitant care during the trial except for the following therapies in the intervention group:

- ezetimibe therapy
- PCSK-9 inhibitors
- any other LDL cholesterol-lowering medication

GPs and pharmacists are advised to avoid these therapies unless there are justified clinical reasons.

5 STATISTICS AND METHODOLOGY

5.1. Non-inferiority margin and sample size calculation

The sample size calculation is based on a non-inferiority design where we test whether discontinuing statins does not result in reduced event-free survival time (primary endpoint) up to a certain degree (non-inferiority margin). The primary effect measure will be the difference of the Restricted Mean event-free Time over 24 months between the two arms (61, 62).

We defined the non-inferiority margin on the absolute scale of integrated risk difference and fixed it at 5% over 24 months of follow-up (63). This can be interpreted as follows: we want to exclude a loss in event-free time of more than 2 ½ weeks per year (or about 1.5 days per month) over a two year observation period (5.2 weeks overall). This difference is considered by the Steering Committee clinically irrelevant (=non-inferiority) given the multimorbid study population with a high event and death risk.

Based on data from our OPERAM trial (59), we calculated the probability of dying from non-cardiac causes at 12 months as 11.6% and the probability for non-fatal and fatal CV events as 9.1%. Simulations with 10,000 runs were used to calculate the sample size. A Weibull distribution was used to simulate event-free survival data (64). Parameters were chosen to account for a flattening of event probabilities over time. Based on the available OPERAM data, the primary event probabilities in the control group at landmark timepoints were as follows: 22% at 12 months, 34% at 24 months, 43% at 36 months; a drop-out rate of 2% over 1 year was observed (59). Sample size calculations were done in Stata (release 15.1) using the *survsim* package for the simulations and the *strmst2* package for calculating Restricted Mean Event-free Time (65). With 1,800 participants, we will achieve a power of 89% in the Intention-To-Treat (ITT) and 83% in the approximated PP analysis set at a one-sided α level=0.025. We performed several sensitivity

analyses assuming higher and lower event rates as well as non-proportional hazards, and power was >80% in all scenarios. The planned interim analysis (see 5.5) will have no relevant influence on the type I and II error rate and therefore, sample size is not adjusted (66).

For the subgroup analysis on the effect on LDL cholesterol, we based the sample size calculation on data for over 75 years old patients from the Cholesterol Treatment Trialists' Collaboration (67). Based on an assumed mean LDL cholesterol concentration of 3.2 mmol/L and a standard deviation of 0.8 mmol/L for the statin stop group, a between-group difference in LDL cholesterol of 0.3 mmol/L can be detected at 80% power with a two-sided alpha of 0.05. As previously described, in the case of continuous outcomes, a trial with ~100 participants per treatment arm is considered a large trial, where baseline variables can be expected to be evenly distributed between treatment arms (68).

For the subgroup of patients undergoing cardiac CT scans and measurement of biomarkers at baseline, we based the sample size calculation on a superiority design where we test whether the treatment effect differs by baseline CAC. Based on an assumed CAC distribution from data in the MESA cohort for asymptomatic men and women over 75 years (69), an assumed increased risk per 1-standard deviation change of baseline CAC score on a logarithmic scale (70), 7% of participants with a CAC score of 0 (71), primary outcome event rate at 36 months as in the STREAM trial, and assumption of no treatment effect, we determined that a fixed sample size of 500 participants provides 80% power (with one-sided alpha of 0.05) to detect an interaction term odds ratio as small as 1.9, corresponding to a traditional relative risk estimate of 1.37 at an assumed event prevalence of 43%, since ORs are overinflated when the outcome is common.(72) The power for analyses using biomarkers on a continuous scale will be similar as or even higher than for CAC score, e.g. for NT-proBNP the simulation showed 80% power to detect a relative risk of 1.3 at a fixed sample size of 500 participants.

5.2 Randomization

Participants are randomized (in a 1:1 ratio) to either discontinuing statin vs. continuing statin, with stratification according to age (categorized into two groups: cut off <75/≥75 years of age), statin intensity (categorized into high, moderate and low intensity, according to the 2018 AHA/ACC guidelines (32)), and time under statin before inclusion, (categorized into two groups: cut off: ≤6/>6 years, as 6 years is the longest follow-up in statin trials published in the CTT metaanalysis; beyond 6 years evidences on elderly under statin is based on simulations) using computer-generated randomly permuted blocks of varying size (67, 73).

Study arm allocation is done using a web-based system which also contains the electronic case report form (eCRF) (Webspirit, hosted by CTU Bern). The randomization list is generated by an independent statistician and only system administrators who are otherwise not involved in trial conduct will have access to them to ensure concealment of allocation.

5.3 Statistical methods for primary and secondary outcomes

The primary statistical analysis of the trial will be done at CTU Bern based on well-established standard operating procedures, using an appropriate statistical software. Details are specified in a statistical analysis plan, to be written at the start of enrolment and to be finalized before 25% of patients are enrolled. The plan determines all necessary data preparation steps (e.g. additional validations, generation of new variables), definitions (e.g. analysis sets), and statistical analyses (e.g. models, outputs such as tables and graphs).

The primary outcome of the trial is analyzed with a flexible parametric survival model with all stratification factors as covariates. The difference in Restricted Mean Event-free Time over 2 years will be the effect measure (61, 74). Two years was chosen as this is the average follow-up time in the trial and a clinically useful timeframe given the elderly patient population with higher mortality. Two analyses sets are used for the primary analysis as described below. Non-inferiority will be declared, if for both ITT and PP analysis sets, the one-sided 97.5% confidence interval does not cross the non-inferiority margin. We acknowledge that any choice for the non-inferiority

margin is to some extent subjective and a margin that is universally agreeable is not achievable especially in this heterogeneous patient population (75, 76). Therefore, we will also present results for various margins with the respective uncertainty (77). Components of the primary outcome and other time-to-event outcomes are analyzed with the same methods as the primary outcome. Effects on time-to-event outcomes may also be presented as hazard ratios. Continuous outcomes will be analyzed using linear regression with baseline values and stratification factors as covariates and mean difference as effect measure. Given the potentially high mortality rate we will also explore joint modelling of continuous outcomes and death (78).

ITT and PP analyses will be performed. The ITT analysis set consists of all randomized patients in the allocated group regardless of any protocol violations. For the PP analysis set, we will first carefully define criteria for protocol adherence and post-randomization factors that might cause confounding/selection bias before trial start to allow for appropriate data collection.(79) For this, we will consider pre- and post-randomization factors that are predictive of adherence, amount of statin intake that constitutes adherence to each arm, cross-overs, other CV active medication, and intercurrent events. PP analyses will be done using g-Methods adapted to estimate Restricted Mean Event-free Time (80).

A separate statistical analysis plan will be developed for the analysis of CAC scores and baseline blood biomarkers in the subsample of subjects undergoing these procedures. The primary analysis will be an ITT analysis using Cox proportional hazards regression modelling to assess the effect modification of continuous CAC score on a linear scale on the relationship between treatment and the primary outcome, taking event time into account. Further analyses will test non-linear relationships and/or include biomarkers instead of CAC score.

Any deviation from the original statistical analysis plan will be described and justified in the final trial report. Full details to the statistical analysis will be described in a statistical analysis plan.

[figure not shown]

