The primary endpoint is a composite endpoint of major non-fatal CV events (non-fatal myocardial infarction, non-fatal ischemic stroke) and all-cause death over a follow-up period of 2 years. All-cause death (and not CV death only) is chosen to account for a possible shift from CV to other causes of death (such patterns were seen in two statin RCTs (8, 9)). The composite endpoint was selected to assess the net clinical benefit in this population with expected high mortality.

Secondary endpoints (see schedule of assessment for time of acquisition):

- Composite endpoint of all-cause death and major non-fatal CV events (non-fatal myocardial infarction, non-fatal ischemic stroke)
- Major CV events (CV death, non-fatal myocardial infarction and non-fatal ischemic stroke) as composite and components thereof
- Total CV events (CV death, non-fatal myocardial infarction, hospitalization for unstable angina, non-fatal ischemic stroke (including TIA) and arterial revascularization (coronary and peripheral urgent and non-urgent revascularization))
- Total composite events (all-cause death, non-fatal myocardial infarction, hospitalization for unstable angina, non-fatal ischemic stroke (including TIA) and arterial revascularization (coronary and peripheral urgent and non-urgent revascularization))
- All-cause death
- Non-CV death
- EQ-5D questionnaire: for general quality of life and possible future cost-effectiveness (44)
- Verbal numeric pain rating score (VNPRS): statin associated muscle symptoms (45, 46)
- Falls
- SARC-F questionnaire: muscle function and sarcopenia (47, 48)
- Girerd Medication adherence scale: general medication adherence

Safety endpoints:

Safety endpoints are collected as primary/secondary endpoints.

Other endpoints (see schedule of assessment for time of acquisition):

- Statin and other lipid-lowering drug intake
- Current medication: Drugs against high blood pressure, antiplatelet drugs, blood thinners, and drugs against diabetes

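### Section 5.3 extends the composite's method to endpoints that leave out all-cause death; used unchanged it implies censoring competing deaths and overstates absolute CV risk, though arm differences move little

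*Protocol*

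**What the plan says.** Section 5.3 of the protocol defines the primary analysis in two sentences: "The primary outcome of the trial is analyzed with a flexible parametric survival model with all stratification factors as covariates", and "The difference in Restricted Mean Event-free Time over 2 years will be the effect measure". It then carries that analysis over: "Components of the primary outcome and other time-to-event outcomes are analyzed with the same methods as the primary outcome". Hazard ratios are optional for these outcomes.

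Section 3.2 defines the primary endpoint as a "composite endpoint of major non-fatal CV events (non-fatal myocardial infarction, non-fatal ischemic stroke) and all-cause death over a follow-up period of 2 years". Its secondary list includes endpoints that leave out all or some deaths: "Major CV events (CV death, non-fatal myocardial infarction and non-fatal ischemic stroke) as composite and components thereof", total CV events, and non-CV death. It also lists all-cause death and total composite events, which include every death.

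Two further places bear on the point. Section 3.2 explains the choice of the composite: "All-cause death (and not CV death only) is chosen to account for a possible shift from CV to other causes of death". Section 5.1 reports, from the earlier trial used for planning, "the probability of dying from non-cardiac causes at 12 months as 11.6% and the probability for non-fatal and fatal CV events as 9.1" (per cent).

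High mortality is taken up in section 5.3 only for continuous outcomes, through exploratory joint modelling. Section 5.7 speaks of cross-overs and intercurrent events and does not mention competing death.

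**The concern.** A death of any cause is an event for the primary composite, so nothing competes with it and its restricted mean is time actually lived without an event. That does not carry over. A participant who dies of cancer can no longer have an MI. A single-endpoint survival model applied unchanged has only one place for that participant: censored at death, as if the MI could still come. The survival curve and its restricted mean then describe a setting in which other deaths do not happen.

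By the protocol's own figures the competing event is the more common one: 11.6% non-cardiac death against 9.1% CV events at 12 months. Section 5.5 names CV events as the main safety concern. Readers will therefore use the absolute CV risks and event-free times to counsel multimorbid patients aged 70 or over, and those figures should refer to people who can die of something else. The protocol also allows that stopping statins may move deaths between causes. If it does, the two kinds of arm contrast differ.

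**Working it through.** **Inputs (protocol 5.1).** Composite event probability 22%, 34% and 43% at 12, 24 and 36 months; Weibull event times; 12-month split of 9.1 (CV events) to 11.6 (non-cardiac death); margin 5% of 24 months = 1.2 months = 5.2 weeks; 900 per arm; one-sided alpha 0.025.

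**Step 1: reproduce the plan's figures.** The cumulative hazards are H(12) = −ln 0.78 = 0.2485 and H(24) = −ln 0.66 = 0.4155. The Weibull shape is ln(0.4155/0.2485)/ln 2 = 0.742. This gives 43.0% at 36 months (stated 43%).

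The 24-month restricted mean is 19.03 months with standard deviation 8.06. The standard error of the difference is 8.06 × √(2/900) = 0.380. Power without censoring is Φ(1.2/0.380 − 1.96) = 88.5% (stated 89%). With 85% of the sample (765 per arm) it is 83.0% (stated 83%). The inputs are therefore usable.

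**Step 2: split the hazard.** CV share w = 9.1/(9.1 + 11.6) = 0.440, assumed constant over time.

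- Cumulative incidence, other deaths competing: w × (1 − S).
- Reported risk, other deaths censored: 1 − S^w.

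At 24 months S = 0.66:

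- 0.4396 × 0.34 = 0.1495, that is 14.9%;
- 1 − 0.66^0.4396 = 0.1670, that is 16.7%.

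The ratio is 1.117, an overstatement of 12%. At 36 months the figures are 18.9% and 21.9%.

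The area under each curve to 24 months is the mean time lost: 2.19 and 2.36 months. At 52/12 weeks per month (the conversion that turns 1.2 months into 5.2 weeks) these are 9.5 and 10.2 weeks.

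**Step 3: sensitivity to the split.** The two cause figures add to 20.7%, not 22%. Taking w = (22 − 11.6)/22 = 0.473 instead gives 16.1% against 17.8% at 24 months, an 11% overstatement.

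**Step 4: arm differences at 24 months.** Let h be the CV hazard ratio and g the hazard ratio for other deaths, both assumed. In the discontinuation arm the cumulative incidence is [wh/(wh + (1−w)g)] × [1 − S^(wh + (1−w)g)], and the censored version is 1 − S^(wh).

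| h | g | Risk difference, competing | Risk difference, censored | Time lost, competing | Time lost, censored |
|---|---|---|---|---|---|
| 1.0 | 1.0 | 0 | 0 | 0 | 0 |
| 1.2 | 1.0 | 2.7 points | 3.0 points | 1.8 weeks | 1.9 weeks |
| 1.3 | 1.0 | 4.0 points | 4.4 points | 2.6 weeks | 2.8 weeks |
| 1.3 | 1.2 | 3.6 points | 4.4 points | 2.4 weeks | 2.8 weeks |
| 1.0 | 0.8 | 0.3 points | 0 | 0.1 weeks | 0 |

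For scale, the binomial standard error of the risk difference in the third row is √(0.1495 × 0.8505/900 + 0.1894 × 0.8106/900) = 1.8 points, so the 0.4-point gap is about a quarter of one standard error.

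**Step 5: non-CV death.** Only CV death competes here, because a participant can die of a non-CV cause after a non-fatal MI or stroke. The documents do not give the fatal share f of CV events, so I assume 20% to 50%, with the non-CV death rate unchanged after a non-fatal event. The censored figure is 1 − 0.66^0.560 = 20.8%. Cumulative incidence is [0.560/(0.560 + 0.440f)] × [1 − 0.66^(0.560 + 0.440f)]: 20.4% at f = 0.2 and 19.9% at f = 0.5. The relative gap is about 2% to 4%.

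No figure is offered for MI or stroke alone, because the documents do not give their shares.

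**The case against.** **Censoring is never written down.** This is true. A flexible parametric model is a model family that can be fitted cause by cause and combined into cumulative incidence, and section 5.3 leaves model details to an SAP that was not available. A reader might infer that the protocol orders competing deaths to be censored, and the text does not support that. What stands is narrower. The protocol fixes both the model and the effect measure for these endpoints. Restricted mean event-free time, as defined for the composite, has no place for a competing death. An SAP that handled competing deaths properly would be departing from section 5.3 as worded.

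**The arm comparison hardly changes.** This is also largely right. On the protocol's own scale the shift is about 0.2 week at a CV hazard ratio of 1.3, and zero when there is no effect on either cause. The single-arm absolute risks carry most of the distortion.

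**A shift between causes of death would still be seen.** A reader might infer that the method hides the shift that section 3.2 has in mind. It does not: CV events, non-CV death and all-cause death are separate endpoints, and a fall in non-CV death shows under either method. In the last row of the table, zero is a legitimate answer to whether the CV hazard itself changed.

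**A valid measure is already foreseen.** A hazard ratio with other deaths censored is a proper cause-specific hazard ratio. Section 5.3 makes it optional, however, while the measure it requires is the affected one.

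**Conclusion.** The point holds as a correction to the secondary time-to-event endpoints that do not contain all-cause death. Used as written, the method would overstate 24-month CV risk in one arm by about 1.7 to 1.8 points (11% to 12% relative) and time lost to CV events by about 0.8 week. Arm differences would change by about 0.2 week or 0.4 points at an assumed CV hazard ratio of 1.3. The gap grows to 0.8 points if other deaths also rise (assumed hazard ratio 1.2). For non-CV death the overstatement is about 2% to 4%. A figure near 9% would require every CV event to be fatal, which the endpoint definitions contradict.

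These sizes assume a cause split that is constant over time, independent cause-specific hazards, and event rates as in section 5.1.

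A reader might also infer that the non-inferiority conclusion is at risk. It is not. The primary endpoint, its decision rule, the sample size and power, the interim monitoring of the primary endpoint, all-cause death and total composite events all count every death and are untouched.

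**What to change.** In section 5.3, limit the shared method to endpoints that contain all-cause death: the primary composite, total composite events and all-cause death itself. Add one sentence for major CV events, MI, stroke, CV death, total CV events and non-CV death. For these, report the 24-month cumulative incidence difference and the difference in restricted mean time lost, with death from other causes as a competing event, together with the cause-specific hazard ratio. Cause-specific flexible parametric models combined into cumulative incidence would keep the present model family and the stratification covariates; the Aalen-Johansen estimator is the non-parametric alternative. For non-CV death, name CV death alone as the competing event. Align the SAP with this wording.

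The cost is a small amount of extra analysis in standard software. No new data are needed, since section 4.3 already records cause of death and section 8.1 already sends deaths and CV events to the blinded event committee.
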